#### 8.3. Analysis of other outcomes

Other outcomes to be investigated include measures of cognitive function, mortality, and the occurrence of adverse events. Comparisons of cognitive function between treatment groups will employ longitudinal data analysis techniques (generalized estimating equation (GEE) regression) described by Liang and Zeger that account for the within-subject correlation. This method generates robust estimates for the variance without relying on specific assumptions about the correlation structure. It also allows for the use of a treatment effect indicator along with adjustment for multiple confounders and treatment effect modifiers in the comparison of the patterns of cognitive decline in

8. Analysis plan

the two treatment groups. The outcome measure in the regression model will be the rate of change from baseline in the cognitive screening scores, calculated at each time that the tests are administered. To protect against influence of outliers, the ranks of the rates of decline will be used for the determination of p-values.

Survival analysis methods will be used to compare mortality in each of the treatment groups to that in the placebo treated group. If mortality is differential by treatment group, further analysis will be done to determine the effect of the differential mortality on the primary analysis of AD incidence.

The frequency and nature of adverse events will be described in two ways. Descriptive analyses will summarize the occurrence in each of the treatment groups of adverse events noting their frequency, severity, and major organ system involvement. Another analysis will focus on prediction and explanation of adverse events using a composite outcome variable. That is, participants' cumulative history of adverse events during the trial will be classified as mild, moderate or severe. The frequency of these outcomes will be formally compared between the treatment groups. Chisquare statistics and related methods for ordinal categorical variables will be used. In addition, logistic regression models will be used to adjust the frequency of adverse events between the treatment groups for imbalances and baseline predictor variables (if any).

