### **Secondary objectives**

- To determine whether the study treatments can attenuate cognitive decline with aging
- To compare the safety of the study treatments with placebo, and with each other, regarding mortality and the occurrence of side effects

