### 5. Recruitment, screening, eligibility evaluation, and enrollment

- Record current use of proscribed and limited-use medications
- Administer the following neuropsychological tests (see section 7.1) to the prospective participant:
  - Modified Mini-Mental State Examination-Epidemiological
  - Hopkins Verbal Learning Test-Revised
- Ask the collateral respondent to rate the participant using the Dementia Severity Rating Scale
- Collect blood and urine for laboratory tests
- Discuss the consent for enrollment and the consent for DNA testing and banking with the prospective participant; the unsigned consent forms will be sent home with those who indicate their willingness to participate.

If entry criteria are satisfied, the prospective participant will be scheduled for an enrollment visit. Prospective participants whose cognitive status does not meet the study entry criteria may be referred for evaluation outside the study.

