### 5.5. Enrollment visit

At the enrollment visit study staff will:

- Review eligibility
- Discuss the consent for enrollment and the consent for DNA testing and banking and ask participant to sign
- Review and record current medications
- Administer the following neuropsychological tests to the participant:
  - Modified Mini-Mental State Examination-Epidemiological
  - Digit Span
  - Generative Verbal Fluency
  - Narratives from the Rivermead Behavioral Memory Test
  - Hopkins Verbal Learning Test Revised
  - Brief Visuospatial Memory Test Revised
  - Self-rating of Memory Functions
  - Geriatric Depression Scale
- Ask the collateral respondent to rate the participant using the Dementia Severity Rating Scale
- Draw blood for APOE determination and DNA banking
- Obtain the randomized treatment assignment
- Dispense study medications and review instructions for medication use
- Review visit schedule, compliance monitoring, and adverse events reporting

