# 8. Analysis plan

### 8.1. General principles

General principles for analysis include the following:

- The primary analysis will be performed according to participants' original treatment assignment (intention to treat), regardless of administered treatment
- All participants, including those who are found to be ineligible after randomization or those who withdraw from the study, will be counted in their assigned treatment group once that treatment assignment has been revealed
- All events following randomization will be counted
- Subjects with missing measures at a particular time will be excluded from analyses that
  require those measures but will not be excluded from other analyses for which data are
  available

Analyses will be done to look for differences in outcome between each of the groups receiving active treatment and the placebo-treated group. Results of analyses will be presented unadjusted and adjusted. Covariates to be used for adjusting treatment group effects will include field site (also a stratification variable), age at entry (a stratification variable in the form of age categories), APOE genotype, gender, and other prospective baseline risk factors chosen with clinical judgment and/or variable selection procedures such as forward selection. Exploratory analyses will be performed in which post randomization data, such as adherence to the assigned treatment regimen or treatment received, will be taken into account. In addition, treatment effects will be examined across various subgroups.

Formal adjustment procedures will not be used for p-values resulting from the comparisons of each of the active treatment groups with the placebo group or from multiple comparisons made during interim monitoring. In the comparisons of the active treatments to placebo, the two treatment comparisons (naproxen sodium vs. placebo and celecoxib vs. placebo) are viewed as tests of separate experimental hypotheses. With respect to interim monitoring, it is to be expected that numerous comparisons of treatment efficacy and safety must be performed over the course of a clinical trial. Rather than to adjust p-values for multiple comparisons, p-values will be interpreted as descriptive statistics of the evidence, and not as absolute indicators for a positive or negative result.

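### The cognitive-decline model does not name the test's own baseline score as a covariate or say how the two pre-randomisation 3MS-E and HVLT-R scores are used, so precision is left to chance.

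*Protocol*

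**What the plan says.** The first secondary objective in section 2 is cognitive: "To determine whether the study treatments can attenuate cognitive decline with aging". Section 8.3 sets its analysis: GEE regression, p-values from ranks, and a response defined as "The outcome measure in the regression model will be the rate of change from baseline in the cognitive screening scores", computed at each test date. The same paragraph says the method permits "adjustment for multiple confounders and treatment effect modifiers in the comparison of the patterns of cognitive decline in" the groups, but lists no covariates.

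The general list is in section 8.1: "Covariates to be used for adjusting treatment group effects will include field site (also a stratification variable), age at entry", then APOE genotype, gender and "other prospective baseline risk factors chosen with clinical judgment and/or variable selection procedures such as forward selection". Section 8.1 adds: "Results of analyses will be presented unadjusted and adjusted". The core covariate set in 8.2 is for AD incidence and contains no cognitive score either.

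Two of the participant tests are given twice before treatment. At the eligibility visit (5.4), under "Administer the following neuropsychological tests (see section 7.1) to the prospective participant", the list is 3MS-E and HVLT-R. At the enrollment visit (5.5), under "Administer the following neuropsychological tests to the participant", both appear again with the rest of the battery, listed ahead of the treatment assignment. The schedule in 6.6 agrees. The word baseline is not defined for the cognitive scores.

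**The concern.** A change score takes the baseline into account by subtraction. That places the measurement error of one baseline score in every later rate for the same person, most heavily in the year-1 rate, where it is divided by only one year. Conditioning on the baseline score removes part of that variance, and a second pre-treatment score of the same test removes more. Randomisation keeps both adjustments unbiased.

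As written, the most prognostic covariate for this outcome is not named. Whether it enters depends on later judgment or a selection procedure. For 3MS-E and HVLT-R, the choice of baseline score is also open. At stake is the chance of detecting a real attenuation of decline. A chance difference in baseline scores between arms would also carry into unadjusted change scores through regression to the mean.

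**Working it through.** **Inputs.** From the protocol: annual cognitive visits (6.1), up to 7 years (Appendix B), 1:1:1.5 allocation of 2,625, so 2,625/3.5 = 750 per active arm and 1,125 on placebo. Allocation cancels from the variance ratios below. The protocol states no SD, correlation, effect size or power for cognition, so there is no figure of its own to reproduce. Assumed: correlations r = 0.5 to 0.9 for a single follow-up; for repeated visits, intercept SD 4-5.5, yearly slope SD 0.7-1.5, error SD 2.4-4. The starting power of 80% (two-sided 0.05) is illustrative.

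**Power conversion.** For variance ratio R, power = Φ(2.802/√R − 1.960), where 2.802 = 1.960 + 0.842.

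**Single follow-up, equal variances.** Change alone has variance 2(1−r)σ²; change adjusted for baseline has (1−r²)σ². The ratio is (1+r)/2.

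| r | ratio | 80% becomes |
|---|---|---|
| 0.5 | 0.75 | 90% |
| 0.7 | 0.85 | 86% |
| 0.8 | 0.90 | 84% |
| 0.9 | 0.95 | 82% |

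**Seven annual rates, equal visit weights.** Let y_t = b0 + b1·t + e_t, with intercept, slope and error SDs s_i, s_s and s_e. A person's mean rate (y_t − y_0)/t over t = 1 to 7 contains b1, the average of e_t/t, and −k·e_0, where k = (1 + 1/2 + … + 1/7)/7 = 2.5929/7 = 0.3704. The follow-up errors contribute s_e²·(1.5118/49) = 0.0309·s_e². Hence:

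- Variance of the mean rate: s_s² + s_e²(0.1372 + 0.0309) = s_s² + 0.1681·s_e².
- Removed by the enrollment score, zero intercept-slope correlation: (k·s_e²)²/(s_i² + s_e²).
- Removed by both scores, zero correlation: k²·s_e²(s_i² + s_e²)/(2s_i² + s_e²).

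Most favourable corner (4, 0.7, 4): variance 0.49 + 2.689 = 3.179. The enrollment score removes 5.927²/32 = 1.098, ratio 0.65. Both scores remove 0.1372 × 16 × 32/48 = 1.463, ratio 0.54.

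Least favourable corner (5.5, 1.5, 2.4): variance 2.25 + 0.968 = 3.218. The enrollment score removes 2.134²/36.01 = 0.126, ratio 0.96. Both scores remove 0.1372 × 5.76 × 36.01/66.26 = 0.429, ratio 0.87.

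Over all eight corners:

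| Weighting (zero correlation) | Covariates | ratio | 80% becomes about |
|---|---|---|---|
| Equal | enrollment score | 0.65-0.96 | 82-93% |
| Equal | both scores | 0.54-0.87 | 85-97% |
| Efficient | enrollment score | 0.91-1.00 | 80-84% |
| Efficient | both scores | 0.86-0.99 | 80-86% |

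Efficient weighting uses the inverse covariance matrix of the seven rates, and so plays down the noisy early ones.

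**Positive intercept-slope correlation c.** The covariance of the enrollment score with the mean rate is c·s_i·s_s − k·s_e². At c = 0.3 in the corner (5.5, 1.5, 2.4) it is 2.475 − 2.134 = 0.341, close to zero. The ratio is then 1 − 0.341²/(36.01 × 3.218) = 0.999, so the enrollment score alone gains nothing there. With both scores and equal weights, the highest ratio over the grid at c = 0.3 is still 0.87; with efficient weights the two-score ratio is 0.91-0.96.

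**The case against.** A reader might infer that the protocol analyses change without the baseline score and discards the second set of scores. The text does not support that. Section 8.3 allows adjustment without listing covariates, the set in 8.1 is open and could admit a baseline cognitive score, and nothing says the eligibility-visit scores go unused. The baseline score is neither named nor excluded. An analysis plan that is not shown may settle both questions, and rate of change is a valid response under randomisation. All of that stands.

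What remains is that the protocol itself fixes the response and the basis of the p-value for this outcome, yet leaves the obvious covariate to judgment or forward selection, with results shown both unadjusted and adjusted. A strong prognostic covariate is better named in advance than chosen after the data are seen.

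The size is also open to challenge, fairly. Section 8.3 names no working correlation, and much of the repeated-measures gain comes from weighting the visits equally. The single-follow-up formula is correct but is simpler than this design. Rank-based p-values make the normal-theory ratios approximate. The two-score gain reaches only 3MS-E and HVLT-R among the participant tests. Their eligibility scores may be truncated by the cognitive exclusion in 3.3 or carry practice effects, which can shrink the gain but does not bias the treatment comparison.

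**Conclusion.** The point holds as one of efficiency on a secondary objective. The response is fixed as rate of change, the test's own baseline score is not a named covariate, and the use of the duplicate 3MS-E and HVLT-R scores is unspecified. Naming them does not worsen precision in a trial of this size. Under the assumed inputs the benefit runs from nothing (enrollment score alone, with efficient weighting or a positive intercept-slope correlation) to a variance ratio of 0.54 (both scores, equal weights, zero correlation).

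Two stronger readings fail. The comparison is not biased: a baseline imbalance would arise by chance, and randomisation balances it in expectation. Nor is any particular loss of power established, because the protocol states no power, SD or correlation for cognition; the 80% is only a reference point.

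**What to change.** Add to section 8.3 that each cognitive-change model includes the enrollment-visit score of the same test as a prespecified covariate, and that the 3MS-E and HVLT-R models also include the eligibility-visit score. State that the enrollment score is the baseline from which change is measured. Use the same covariates when ranks of the rates are analysed, so that the p-value and the estimate rest on the same adjustment. Keep field site and age as already listed in 8.1.

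The cost is a sentence or two of analysis text. The scores are already scheduled before assignment, and entry requires both visits, so no data, visits or participants are added.

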#### 12. Protection of human subjects

#### 12.3. Risks and potential benefits to participants

**Risks**: There are risks to participation in ADAPT for each treatment group. Like all participants, those assigned to placebo will be asked to limit the use of NSAIDs and other medications (see section 3.3). Thus, participants in this group may have an increased burden of pain or inflammation, for example.

Participants assigned to receive naproxen sodium or celecoxib may experience adverse effects of the study drug, such as water retention, increased blood pressure, stomach irritation, gastrointestinal bleeding, anemia, renal toxicity, or hepatotoxicity. The risk of serious adverse events is expected to be higher in the naproxen sodium group than in the celecoxib group.

The above risks are outlined in the Participant Consent Statement for Enrollment (see Appendix C). Participants are told that they may withdraw from the study at any time and that they may stop the study drug in order to take proscribed medications. Safety monitoring is described in section 12.4.

**Potential benefits**: If one or both of the active study treatments are found to be efficacious, participants taking the efficacious treatment(s) may benefit from delayed onset or prevention of AD. It also is possible that participants receiving naproxen could benefit from a lower risk of heart attack, stroke, and certain cancers, although these effects are still under investigation.

All participants may benefit from the regular, ongoing, medical monitoring and referrals (when indicated) that they will receive in ADAPT. Those who develop dementia while in the trial may benefit from early diagnosis, which could facilitate appropriate treatment and care. In addition, all participants may benefit from the satisfaction of contributing to medical knowledge.

Alternatives to participation: Because ADAPT is a primary prevention trial, there is no direct alternative to participation. Other primary prevention trials are in progress, but the geographical location of the participating sites for the most part does not coincide with that of the ADAPT sites. Because the study medications are available either over the counter (naproxen sodium) or by prescription (celecoxib), people interested in the prevention of AD could self-medicate. However, given the unknown safety and efficacy of such use, it is not an advisable alternative to study participation.

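### Section 8.3 omits the between-drug mortality comparison that the objectives promise, and formally compares adverse events on one severity grade that is insensitive to a rare serious harm

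*Protocol*

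**What the plan says.** **Objective.** Protocol section 2, repeated in Appendix B, sets the safety aim: "To compare the safety of the study treatments with placebo, and with each other, regarding mortality and the occurrence of side effects".

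**Mortality analysis.** Section 8.3: "Survival analysis methods will be used to compare mortality in each of the treatment groups to that in the placebo treated group". Section 8.1 frames the analyses in the same way, as a search for "differences in outcome between each of the groups receiving active treatment and the placebo-treated group".

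**Adverse events.** Section 8.3 gives two analyses.
- The first is descriptive: "Descriptive analyses will summarize the occurrence in each of the treatment groups of adverse events noting their frequency, severity, and major organ system involvement".
- The second is a composite. Each participant's "cumulative history of adverse events during the trial will be classified as mild, moderate or severe", and then "The frequency of these outcomes will be formally compared between the treatment groups", by chi-square and related ordinal methods.

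Logistic models follow, to adjust adverse-event frequency for imbalances and baseline predictors. Section 8.3 does not say whether their outcome is the composite or particular events.

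**Expected harms.** Section 12.3 names "adverse effects of the study drug, such as water retention, increased blood pressure, stomach irritation, gastrointestinal bleeding, anemia, renal toxicity, or hepatotoxicity" and expects more serious adverse events on naproxen sodium than on celecoxib.

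**The concern.** The two parts differ in kind.

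The first is a mismatch inside the protocol. The objective asks for a drug-versus-drug comparison of mortality, and the analysis section names its mortality contrasts and leaves that one out. An analyst who follows section 8.3 would not produce it.

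The second is a choice of method. A single cumulative grade drops the type of event, its timing and its recurrence. In people aged 70 or over who are followed for up to 7 years, many in every group may be graded severe for reasons unrelated to the drug. A real excess of a rare serious event, such as gastrointestinal bleeding, then moves the severe share very little. The harms that section 12.3 lists would be visible in tables, but no comparison with an estimate and an interval is specified for any of them.

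**Working it through.** **Inputs.** From sections 3.2 and 3.4: N = 2,625 at 1:1:1.5, so 750 per drug and 1,125 on placebo; mortality 4% in year 1, multiplied by 1.085 each year; loss 5% per year; drop-out from active drug 15% in year 1 and 5% per year after; placebo drop-in 2.5% per year. The background of 0.5% per year for serious gastrointestinal events is in the revised consent text in the Document history for version 1.4, which also reports 0.6% per year observed in all trial participants. **Assumed:** 1.0% per year on active drug (a scenario; the only document figure like it is in superseded consent text), the placebo share graded severe (not in the documents), and a full 7 years of potential follow-up.

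**The plan's own figure.** The protocol gives no power for safety. Its efficacy figure reproduces: Schoenfeld's formula for a hazard ratio of 0.7 with 40:60 allocation needs (1.96 + 0.8416)² / (0.24 × ln(0.7)²), or 258 events. The stated rates yield 251 to 255 events, power about 0.79 to 0.80. This reads the 30% as the net intention-to-treat reduction; the present point does not depend on that.

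**Follow-up.** The share still followed is multiplied each year by (1 − mortality) × 0.95. Averaging the start and end of each year and summing over 7 years gives 5.06 person-years per participant, with 48% still followed at year 7.

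**Mortality, drug versus drug.** Summing (share at risk) × (mortality) × 0.975, where 0.975 allows for half a year's loss, gives 0.26 deaths per participant: about 195 per drug group, 390 in total. The hazard ratio detectable with 80% power is exp(2.80 / √(390 × 0.25)) = 1.33. Each drug against placebo: exp(2.80 / √((195 + 292) × 0.24)) = 1.30.

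**Gastrointestinal events, event-specific.**
- Placebo: 1,125 × 5.06 × 0.005 = 28.4. Active: 750 × 5.06 × 0.010 = 37.9.
- SE(log HR) = √(1/28.4 + 1/37.9) = 0.248. Power = Φ(0.693/0.248 − 1.96) = 0.80 (0.79 by Schoenfeld's formula).
- Other scenarios, by Schoenfeld's formula: 0.57 for 0.6% versus 1.0%; 0.32 for 0.5% versus 0.75%.
- With drop-out and drop-in (mid-year changes, rates switching between 0.5% and 1.0%), about 78% of active person-years are on drug and 7.4% of placebo person-years are on an NSAID. Active: 750 × 5.06 × 0.005 × 1.78 = 33.7. Placebo: 1,125 × 5.06 × 0.005 × 1.074 = 30.6. Rate ratio 1.66, SE 0.250, power about 0.52.

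**The same excess through the share graded severe.** Cumulative risks are 1 − exp(−5.06 × 0.005) = 2.5% and 1 − exp(−5.06 × 0.010) = 4.9%. If a share b of placebo participants is severe and the events are independent of other severe events, the active share is 1 − (1 − b) × 0.951/0.975. For b = 30% that is 31.75%: difference 0.0175, SE 0.0218, two-sided power 0.13.

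| Placebo share graded severe (assumed) | 10% | 20% | 30% | 50% | 70% |
|---|---|---|---|---|---|
| Power, no drop-out or drop-in | 0.32 | 0.18 | 0.13 | 0.08 | 0.06 |
| Power, with drop-out and drop-in | 0.19 | 0.11 | 0.09 | 0.07 | 0.06 |

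**Checks (no drop-out or drop-in).**
- If deaths count as severe (an assumption), b is at least 26% and power is 0.14.
- If excess events never overlap with other severe events, power is 0.38 at b = 10% and 0.18 to 0.25 from 20 to 70%.
- An ordinal test on all three grades gives 0.14 to 0.07 for b from 10 to 50%.
- A common, milder harm fares better. With 37/37/26% mild/moderate/severe, moving 10, 15 or 20% of mild participants to moderate gives ordinal power of 0.19, 0.36 or 0.57.

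**The case against.** The strongest reply is that event-specific endpoints, their models and the grading rule usually belong in a statistical analysis plan, which may exist. That answers missing detail. It does not answer a protocol that names its mortality contrasts and omits one in its objectives, or that states which adverse-event variable is compared formally and which data are only described.

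Other points stand and limit the claim. A reader might infer the following, and the documents do not support it:
- **That the composite is the only formal test.** The logistic models may cover particular events, so it is only the comparison that is called formal.
- **That the plan is nearly blind to all the named harms.** The calculation covers one rare serious harm on an assumed background. Section 12.3 also lists commoner effects such as raised blood pressure, where the composite may do better. Organ-system tables by group are planned, and the unmasked monitoring committee in section 9 sees adverse-event and mortality comparisons.
- **That the trial could reliably show a doubling and would report no difference.** With the protocol's own non-adherence, event-specific power is about 0.52. Section 8.1 also treats p-values as descriptive and not as a verdict.
- **That ignoring time at risk biases the comparison.** Concurrent stratified randomization balances entry dates; follow-up would differ only through differential death or loss, and none is shown.
- **That drug-versus-drug comparison is absent throughout.** The adverse-event comparison is between the treatment groups without restriction. The gap is in mortality.

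**Conclusion.** Both parts hold in limited form. The mortality mismatch is certain from the text: a stated secondary objective lacks its planned comparison, although the protocol's rates would make that comparison informative, with about 390 deaths and 80% power for a net hazard ratio of about 1.33.

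The adverse-event choice is a real weakness for rare serious harms. In the gastrointestinal illustration the composite loses more than half the power of an event-specific comparison at every background share examined, with or without non-adherence. The exact loss rests on the assumed 1.0% rate and on a severe share that the documents do not give. The result should not be carried over to common, milder harms. Changing section 8.3 is worthwhile; nothing here suggests that harms would go unseen during the trial.

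**What to change.** In section 8.3:

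1. Add naproxen sodium versus celecoxib to the mortality survival analysis, so that it matches section 2 and Appendix B.
2. Add event-specific intention-to-treat comparisons, each with a 95% confidence interval, for the serious harms named in section 12.3 (such as gastrointestinal bleeding and renal toxicity) and for all serious adverse events. Use time to first event where dates are recorded and a risk ratio otherwise. Run each drug versus placebo and drug versus drug.
3. State the outcome of the logistic models.
4. Keep the cumulative severity grade as a summary.

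The mortality contrast is one extra comparison in an analysis already planned. The event-specific work is mainly analysis, but the protocol does not show that event dates and classifications are recorded for every harm, so this needs checking. The downside is several safety estimates without multiplicity control, which section 8.1 already accepts.
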